5.7.1.1 Definition and assessment of COPD exacerbations

For the purpose of this study, a COPD exacerbation is defined as a complex of lower respiratory events / symptoms (increase or new onset) related to the underlying COPD, with duration of three days or more.

A complex of lower respiratory events / symptoms is defined as at least two of the following:

- Shortness of breath
- Sputum production (volume)
- Change in sputum colour
- Cough
- Wheezing
- Chest tightness

“Onset of exacerbation” will be defined as the onset of first recorded symptom. The “end of exacerbation” will be decided by the investigator based on clinical judgment.

Exacerbations will be classified as follows:

Mild:	a new prescription or increased usage of maintenance bronchodilator only
Moderate:	patient receiving an exacerbation-related prescription of oral corticosteroids and/ or antibiotic not requiring hospitalisation
Severe:	COPD-related hospitalisation including emergency room visit

In the situation of hospitalisation associated with COPD exacerbation, the information collected should include the start date of all COPD-related hospitalisations as well as the discharge date from the hospital or equivalent.

Information regarding exacerbations will be collected by the investigators during the visits and telephone calls, and recorded in the eCRF. During all telephone calls and clinic visits, the same questions regarding exacerbation will be addressed for collecting exacerbation-related details and then recorded in the eCRF.

For all patients (completed/discontinued) the COPD exacerbation collection period of interest will be the screening and observational phase ending at Visit 7/ discontinuation visit.

If subjects are hospitalized, the study site will be responsible for collecting and reviewing pertinent medical records so that an informed judgment can be made as to the primary cause for admission.

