6.1.1.4 COPD exacerbation and respiratory tract infection

If a patient experiences a COPD exacerbation or respiratory tract infection during the screening period, Visit 2 will be postponed until 4 weeks following recovery from the exacerbation or infection. Screening period may be extended up to eight weeks if the patient experiences a COPD exacerbation or respiratory tract infection during the screening period (refer to [Section 4.2.2.1](#)).

If patient has a COPD exacerbation or respiratory tract infection during the observational period, study visits will be rescheduled. Please discuss with the Local Clinical Monitor.

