7.7 DETERMINATION OF SAMPLE SIZE

Due to the exploratory nature of the study, power computations are focused on attaining desired precisions for biomarker estimates and relevant clinical assessments in all COPD patient groups except for the A1ATD group.

Calculations are performed in SAS 9.3 using PROC POWER procedure. By assuming up to a 20% dropout rate, at least 100 subjects are expected to contribute to the analysis at the end of 3-year study period. The computations are thus based on 100 subjects in each COPD patient group.

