5.1 PRIMARY ENDPOINT(S)

The main outcome measures of the study are described in CSP Section 5.1.1. To clarify the CSP wording, the main outcomes are also listed here:

- Absolute change from baseline in lung density based on PD15 adjusted for lung volume (ALD) [g/L/year] (up to week 156) (for definition of ALD see Section 9.2)
- Annual rate of lung function decline based on FEV1 [mL/year] (up to week 156)
- Number of exacerbations during study (up to week 156)
- Duration of exacerbations during study [days] (up to week 156)
- Occurrence of an at least moderate exacerbation during study (up to week 156)
- Occurrence of a severe exacerbation during study (up to week 156)

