7. PLANNED ANALYSIS

The labelling and display format of statistical parameters will follow BI standards [10]. For End-Of-Text tables, the set of summary statistics is: N, Mean, SD, Min, Q1 (lower quartile), Median, Q3 (upper quartile) and Max. In descriptive statistics tables, all statistical parameters will be rounded to one additional digit than the raw individual value.

Tabulations of frequencies for categorical and ordinal data will include all possible categories and will display the number of observations in a category as well as the percentage (%) relative to the respective group (unless otherwise specified, all subjects in the respective subject set whether they have non-missing values or not). The category missing will be displayed only if there are actually missing values. Percentages will be rounded to one decimal place.

Subject sets for the planned analyses are displayed in Table 6.3: 2. Subject data listings (SDLs) will be based on the Observed subjects set.

If applicable, conversion from days to weeks, months and years will be as follows:

- Weeks = Days / 7
- Months = (Days * 12) / 365.25
- Years = Days / 365.25

Descriptive statistics will be presented, using both the OBS and PPSBM subject analysis sets, for the following demographic and baseline characteristics, by diagnosis group and for all COPD GOLD groups combined (GOLD 1-3). A1ATD group will be presented separately. See Section 6.7 for definition of baseline measures.

Subjects who have not prematurely discontinued the study should be displayed as "Still in study". Subjects who completed week 104 and didn't consent for the 3rd year expansion of the observational period, they will be displayed as "Completers".

Demographic data: Sex, ethnicity, race, age (years), age (categories), height [cm], weight [kg] and BMI [kg/m²].

Disease characteristics:

- Smoking history in pack years
- Subgroups defined in Section 6.3
- Medical history for COPD (by type of medical disorder)
- Symptom questionnaires: defined in Section 5.3.4

- Spirometry: parameters listed in Section 5.3.1.1
- Body plethysmography: parameters listed in Section 5.3.1.2
- DLCO: parameters listed in Section 5.3.1.3
- SpO2 [%]
- BODE index
- 6 minute walk test: parameters listed in Section 5.3.7.3
- Soluble biomarkers: parameters listed in Section 5.3.2
- biomarkers:
 - Qualitative and Quantitative CT:

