 g_i = random slope effect for subject i

 φ_i = slope coefficient of the effect of SG j

 t_{ik} = time of measurement k for subject i, k= 1, 2,... 7

 e_{ik} = the random error associated with the kth visit of the ith subject. Errors are independent and normally distributed with mean 0 and variance σ^2 , and uncorrelated with a_i and g_i .

 Σ = a 2x2 unstructured covariance matrix

The Kenward-Roger approximation will be used to estimate denominator degrees of freedom and adjust standard errors. Significance tests will be based on least-squares means using a two-sided $\alpha = 0.05$ (two-sided 95% confidence intervals). The primary subject-group comparison of slopes will be assessed through the SG-by time interaction coefficient.

SAS procedure PROC MIXED is implemented for this analysis. SAS code can be found in Section 9.5.2.

Number of exacerbations during study (up to week 156)

This endpoint will be summarized descriptively by the following categories: 0 vs. 1 vs. \geq 2.

Duration of exacerbations during study [days] (up to week 156)

This endpoint will be calculated by the sum of episodes during the study and will be summarized descriptively. Duration of exacerbations will be summarized for subjects with at least one exacerbation.

Occurrence of an at least moderate exacerbation during study (up to week 156)

This endpoint will be summarized by the number of patients with an at least moderate exacerbation during study falling into the following categories 0 vs. 1 vs. \geq 2.

Occurrence of a severe exacerbation during study (up to week 156)

This endpoint will be summarized by the number of patients with a severe exacerbation during study falling into the following categories $0 \text{ vs. } 1 \text{ vs. } \ge 2.$

Definitions of severity of exacerbations can be found in Section 5.7.1.1 of the CSP.

[figure not shown]

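### The visible SAP tabulates the exacerbation main outcomes without follow-up time, so unequally observed subjects are mixed; its partial-date rule can also put an exacerbation's end before its start

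*SAP*

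**What the plan says.** SAP 5.1 lists six main outcomes. Four are exacerbation outcomes: number, duration, occurrence of an at least moderate event, and occurrence of a severe event. Each carries the same horizon, for example "Number of exacerbations during study (up to week 156".

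SAP 7.4.1 gives the analysis. For the number: "This endpoint will be summarized descriptively by the following categories: 0 vs. 1 vs" two or more. The two severity outcomes use the same three categories. For duration: "This endpoint will be calculated by the sum of episodes during the study and will be summarized descriptively", restricted to subjects with at least one event. The opening of SAP section 7 sets the percentage base as "all subjects in the respective subject set whether they have non-missing values or not", unless stated otherwise.

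Unequal follow-up is expected. Protocol 7.7 states: "By assuming up to a 20% dropout rate, at least 100 subjects are expected to contribute to the analysis". SAP section 7 also describes subjects who finish Week 104 and do not "consent for the 3rd year expansion of the observational period, they will be displayed as" completers.

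On which events count, Protocol 5.7.1.1 says that "the COPD exacerbation collection period of interest will be the screening and observational phase ending at Visit 7/ discontinuation visit". Protocol 3.3.5.1 and 6.2.2 place the discontinuation visit at the next scheduled visit. Protocol 3.1 and 6.2.2 also collect exacerbation status by telephone after discontinuation, up to the date Visit 7 would have fallen, if the subject agrees again.

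On dates, SAP 6.6.2 names exacerbation dates. It calls for the midpoint of the possible interval, then fixes that as day 15 (month known) or 1 July (only year known).

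**The concern.** A count or a summed duration depends on how long a subject was watched. An early leaver without an event stays in the denominator, and nothing visible in the SAP separates that subject from one who was event-free for three years. In the same section, the FEV1 outcome is modelled against measurement time; the exacerbation outcomes have no counterpart. A reader comparing GOLD groups, or comparing this cohort with another, cannot tell from these tables how much observation lies behind each column.

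The counting window is also open. The visible SAP does not say whether screening events or telephone-collected events enter the tables, so two programmers could produce different results for a main outcome.

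The date rule feeds the duration outcome directly. It can yield a zero or negative length, or one below the three days that Protocol 5.7.1.1 requires of an exacerbation.

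**Working it through.** **The plan's own figure.** 125 × (1 − 0.20) = 100 per COPD group, as Protocol 7.7 states. No precision figure is given for exacerbations.

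**Inputs.** From the documents: horizon 3 years, loss up to 20%, clinic visits at Weeks 12, 26, 52, 104 and 156. Assumed, because the documents give no figures: rates r = 0.3, 0.5 and 1.0 per patient-year, Poisson or negative binomial (NB) counts with dispersion 1, and leaving times uniform on 0.25 to 2.75 years (mean 1.5).

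**Formulas.** Poisson: P(≥2 | t) = 1 − e^(−rt)(1 + rt). NB: P(≥2 | t) = 1 − 1/(1 + rt) − rt/(1 + rt)². The full-follow-up value has t = 3. The observed value is 80% at t = 3 plus 20% averaged over the leavers' follow-up.

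**No leaver attends a discontinuation visit.** Mean follow-up = 0.8 × 3 + 0.2 × 1.5 = 2.70 years, so 10% of events are missed.

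**Every leaver attends at the next scheduled clinic visit.** Leavers are then followed to 0.5, 1, 2 or 3 years in proportions 10%, 20%, 40% and 30%, mean 1.95 years. Mean follow-up = 2.4 + 0.2 × 1.95 = 2.79 years, so 7% are missed.

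| Model, rate | P(≥2) at 3 y | None attend (fall) | All attend (fall) |
|---|---|---|---|
| Poisson 0.3 | 22.7% | 19.9% (2.9) | 20.7% (2.0) |
| Poisson 0.5 | 44.2% | 39.0% (5.2) | 40.6% (3.7) |
| Poisson 1.0 | 80.1% | 72.5% (7.6) | 74.9% (5.2) |
| NB 0.3 | 22.4% | 19.9% (2.5) | 20.7% (1.8) |
| NB 0.5 | 36.0% | 32.4% (3.6) | 33.5% (2.5) |
| NB 1.0 | 56.3% | 51.7% (4.6) | 53.1% (3.1) |

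**Variations, no visit attended.**
- Four weeks of screening counted at the full rate: fall of 1.9 to 6.3 points. This overstates the offset, because "Visit 2 will be postponed until 4 weeks following recovery from the exacerbation or infection", which keeps recent events out of the run-up to Visit 2. Simulating that rule gives 1.9 to 6.9.
- Loss of 10%, or half of later events captured by telephone and counted: 1.3 to 3.8. All captured and counted: none.
- All 20% stopping at Week 104 instead: 1.7 to 4.1.
- Leavers with twice the event rate: true mean 0.8 × 3r + 0.2 × 6r = 3.6r, observed 2.4r + 0.2 × 1.5 × 2r = 3.0r, so the count is 17% low. The crude rate, 3.0r/2.7 = 1.11r, is still below the true 1.2r.

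**Between groups.** An assumed 10% v 20% loss creates a 1.3 to 3.8 point difference. The 95% half-width for two groups of 125 is 1.96 × √(2p(1 − p)/125), or 10.4, 12.4 and 9.9 points at p = 0.23, 0.50 and 0.80.

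**Dates.** Start 20 March with end known only as March becomes 15 March, five days early. Start 10 September with only the same year known for the end becomes 1 July, 71 days early. Two dates known only to the same month give 0 or 1 day.

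Simulation of 400,000 events (30-day months, uniform start, lognormal length with log SD 0.6, minimum 3 days, assumed medians 7, 10 and 14 days):

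| | Month-only end | Month-only start |
|---|---|---|
| Zero or negative length | 26.9 / 18.9 / 11.7% | 23.7 / 16.3 / 9.7% |
| Mean error, current rule | about −0.5 day | about +0.5 day |
| Mean absolute error, current rule | 7.5 days | 7.5 days |
| Mean absolute error, nearest feasible date | 5.4 / 6.1 / 6.7 | 5.7 / 6.4 / 6.9 |

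**The case against.** The outcome label covers events during the study, and its Week 156 limit can be read as a maximum. Protocol 6.2.2 treats Visit 7 or the discontinuation visit as the end of the study period, which agrees with 5.7.1.1. A reader might infer that the tables are mislabelled 156-week burdens; the label does not promise that. This stands, and makes the point mainly one of comparability.

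A reader might also see a flat contradiction between 5.7.1.1 and the telephone follow-up. The two can coexist if the calls are a separate status collection. What remains is that the visible SAP does not say whether those events are tabulated.

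Disposition tables, the Week 104 completer category and the COVID-19 summary will show some unequal follow-up, and SAP 7.9 lists event dates. None gives person-time or a rate. SAP 5.3, 7.6 and 9 are not shown, so it cannot be concluded that no adjusted exacerbation analysis exists.

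On dates, the midpoint wording could be read as bounded by the known date. The fixed values that follow do not do that, and the clause on individual assessment covers other cases, not clearly this one. It is fair that the number of partial dates is unknown. A reader might infer a biased mean duration; the simulation does not support that, since the error lies in individual values.

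**Conclusion.** The point holds in a limited form. As visible, SAP 7.4.1 mixes subjects with different follow-up and gives no figure to show it. If counting stops at Visit 7 or the discontinuation visit, and the table is read as a 156-week burden, about 7% of events are missed with full attendance at that visit and 10% with none. The fall in the share with two or more events is 1.8 to 5.2 or 2.5 to 7.6 points. These sizes rest on assumed rates and leaving times and on the plan's maximum loss. They shrink if screening events count, and shrink or vanish if telephone events count.

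It would go too far to say that group comparisons are spoiled or that a test fails. The artefact at the assumed 10% v 20% loss is within sampling error, these outcomes are descriptive, and Protocol 7.2 makes all tests exploratory.

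The date rule, as written, can put impossible values into a main outcome; how often is unknown. Priority: minor to moderate.

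**What to change.** 1. Beside the existing tables, report follow-up time and exacerbation events and days per patient-year by COPD group. State that the rate assumes leaving is unrelated to exacerbation risk; the doubled-rate example shows what it cannot repair. A count model with a log follow-up offset is optional.
2. Reconcile Protocol 5.7.1.1 with 3.1 and 6.2.2, and say in the SAP whether screening and telephone-collected events count. Match person-time to the events counted, ending it at the discontinuation visit when one is attended and otherwise at last contact. If the calls yield no event counts or dates, stop both at that point.
3. In SAP 6.6.2, keep day 15 or 1 July when compatible with the known date. Otherwise take the nearest feasible date: an end no earlier than start + 2 days and no later than the reporting contact, with the mirror rule for a missing start. Report how many dates were imputed. A midpoint bounded by the known start is not advised: for missing ends it lengthened mean duration by 3 to 5 days in the simulation.

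The cost is some SAP wording and one table from data already collected. The date check moves the mean duration of imputed events to 0.3 to 1.6 days above truth for a missing end and 1.2 to 2.3 for a missing start. In return, impossible values go and per-event error falls.

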5. VARIABLES AND THEIR ASSESSMENT

5.1 SUMMARY OF STUDY OUTCOMES AND ASSESSMENTS

5.1.1 Main outcome measures

- Change of lung density assessed by CT over the course of the study
- Lung function decline over the course of the study
- Number, duration and severity of exacerbations during the course of the study

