7.3.1 Primary analyses

7.3.1.1 Descriptive and Summary Statistics

Continuous variables are characterized by their distributional summary statistics. Ordinal, counts, and categorical variables are summarized by counts and frequencies. Statistics are computed for each subject group (healthy subjects, GOLD 1, GOLD 2, GOLD 3, and COPD with A1ATD), and for all subjects combined when appropriate.

For variables measured for more than once during the course of the study, descriptive statistics are provided at each time point. In addition, if they are continuous, changes from baseline are calculated by subtracting baseline values from post-baseline values. Summary statistics are presented for each change by each subject group and by all subjects combined. Their 95% confidence intervals are also presented.

Summary plots such as histograms, barplots, or boxplots are produced as visual aids for understanding the distributions of these variables.

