7.8.1 Adverse events (procedure related)

Only procedure related AEs are recorded and analyses will be performed on the OBS subjects.

These events will be coded using the most recent version of MedDRA.

The analyses of adverse events will be descriptive in nature. All analyses of AEs will be based on the number of subjects with AEs and not the number of AEs.

For analysis, multiple AE occurrence data on the electronic case report form (eCRF) will be collapsed into one event provided that all of the following applies:

- All AE attributes are identical
- The occurrences were time-overlapping or time-adjacent (time-adjacency of 2 occurrences is given if the second occurrence started on the same day or on the day after the end of the first occurrence)

For further details on summarization of AE data, please refer to Analysis and Presentation of AE data from clinical trials '[14] and "Handling of missing and incomplete AE dates" [7].

Other significant AEs will be reported and summarized according to ICH E3 [16] criterion. Thus, AEs classified as 'other significant' will include those non-serious adverse events with:

- (i) 'action taken = discontinued from study', or
- (ii) marked hematological and other lab abnormalities, or lead to significant concomitant therapy as identified by the Clinical Monitor / Investigator at an MQRM or a RPM.

An overall summary of adverse events will be presented by subject group.

The frequency of subjects with adverse events will be summarized by subject group, primary SOC and PT. Separate tables will be provided for subjects with serious adverse events and with other significant adverse events.

The SOCs will be sorted according to the standard sort order specified by the European Medicines Agency (EMA), PTs within SOC will be sorted by descending relative frequency.

For disclosure of AE data on ClinicalTrials.gov, the frequency of subjects with non-serious AEs (procedure related) occurring with an incidence of greater than 5 % (in preferred terms) will be summarised by primary SOC and PT. The frequency of subjects with SAEs will also be summarised.

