7.9 MEDICAL EVENTS OF SPECIAL INTEREST (MESIS)

Specific disorders related to the underlying COPD disease as defined in the CSP, Section 5.7, will be collected during the study. MESI are analysed per AE standards based on PPSBM subjects. The frequencies of these MESIs will be summarised by disorder and intensity following the same order as in the eCRF. A separate listing by subject group and disorder will be created including additional information of start/end date, outcome, provided therapy, and intensity of the event.

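### The number of exacerbations, a main outcome, is summarised in SAP 7.4.1 only as 0, 1 or at least 2, so the planned table gives no mean or rate per group

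*SAP*

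**What the plan says.** Protocol 5.1.1 lists as a main outcome "Number, duration and severity of exacerbations during the course of the study". SAP 5.1 turns this into four endpoints up to week 156: the number, the total duration in days, the occurrence of an at least moderate exacerbation, and the occurrence of a severe one.

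For the number, SAP 7.4.1 states: "This endpoint will be summarized descriptively by the following categories: 0 vs. 1 vs", with two or more as the top class. The two occurrence endpoints use the same classes. Duration stays numeric: "This endpoint will be calculated by the sum of episodes during the study and will be summarized descriptively", restricted to subjects with at least one exacerbation. The other two main outcomes, adjusted lung density and FEV1, get mixed models with 95% confidence intervals.

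Two other places touch the count. Protocol 7.3.1.1 gives the general rule: "Ordinal, counts, and categorical variables are summarized by counts and frequencies". Exacerbations are also medical events of special interest (Protocol 5.7.1), and for these SAP 7.9 says: "MESI are analysed per AE standards based on PPSBM subjects".

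**The concern.** The endpoint is a number, but its stated summary does not return one. Over up to three years the top class need not be a thin tail. It can hold a large part of a COPD group and most of the events, and it does not separate occasional from frequent exacerbators. Two diagnosis groups that differ mainly among patients with several events would look alike in the table.

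The study asks whether biomarkers relate to COPD progression. If the three classes were carried into group or biomarker contrasts, information on one main outcome would be given up for no stated reason.

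**Working it through.** **1. The plan's own figures.** Protocol 7.7 gives no rate, precision or power for exacerbations. It does give the group size: 125 × (1 − 0.20) = 100 per COPD group, used below. Its correlation table reproduces. For r = 0.30, 15 partialled variables and n = 100, take N = 85: (atanh 0.30 + 0.30/(2 × 84)) × √82 = 2.82, and Φ(2.82 − 1.96) = 0.805, as stated. That table covers continuous variables and says nothing about this endpoint.

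**2. Do other visible tables restore the number?** No. Event-of-interest tables follow adverse-event standards, and SAP 7.8.1 says: "All analyses of AEs will be based on the number of subjects with AEs and not the number of AEs". They count patients. What does survive is the raw material: "A separate listing by subject group and disorder will be created including additional information of start/end date, outcome, provided therapy, and intensity of the event".

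**3. What the three classes hide.** Assume negative-binomial counts with mean μ and variance μ + kμ². Then P(0) = (1 + kμ)^(−1/k), P(1) = P(0) × μ/(1 + kμ), and the mean within the top class is (μ − P(1))/P(≥2).

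- μ = 0.75, k = 1: 57% / 25% / 18%; top-class mean 2.75.
- μ = 1.5, k = 1: 40% / 24% / 36%; top-class mean (1.5 − 0.24)/0.36 = 3.5.
- μ = 2.4, k = 0.7: P(0) = 2.68^(−1.43) = 0.245 and P(1) = 0.245 × 2.4/2.68 = 0.219, so 54% are in the top class; its mean is (2.4 − 0.219)/0.536 = 4.1.

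A 40/24/36 table bounds the mean only from below: 0.24 + 2 × 0.36 = 0.96. With a top-class mean of 3.5 the overall mean is 0.24 + 3.5 × 0.36 = 1.50; with 6 it is 2.40. All three means give the same table.

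**4. Follow-up.** Protocol 7.7 allows for up to 20% dropout, and SAP section 7 shows subjects who finished week 104 without consenting to the third year as completers. At 0.5 events per year and k = 1, two years of follow-up (μ = 1.0) put 25% in the top class and three years (μ = 1.5) put 36% there. A bare mean would carry the same distortion, so the added summary must use person-time.

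**5. Power, if a contrast were made on the classes.** Two groups of 100, rate ratio 1.5, k = 1, equal three-year follow-up, two-sided 0.05, 3000 simulations per row. The rate is that of the lower-rate group. Power in %:

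| Rate/year | NB test, count | Trend test, classes | Mann-Whitney, count | Mann-Whitney, classes |
|---|---|---|---|---|
| 0.25 | 49.9 | 39.6 | 41.3 | 38.2 |
| 0.5 | 62.0 | 38.8 | 50.0 | 39.3 |
| 1.0 | 71.7 | 34.2 | 60.0 | 35.3 |
| 1.5 | 76.1 | 27.6 | 63.8 | 29.0 |

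Simulated type I error was 3.9% to 6.0%. The gap is 10, 23, 38 and 48 points for the negative-binomial test against the trend test, and 3, 11, 25 and 35 points for the same rank test on both scales. Over k = 0.5 to 2 the first gap runs from about 9 points (61.6 vs 52.8) to 56 (93.7 vs 38.2), and the second from about 3 (26.8 vs 24.3) to 47 (88.2 vs 41.2). A separate simulation at 3-year means of 0.5 to 0.75 and rate ratios 1.5 to 2.0 put the loss at 2 to 11 points. For a biomarker with Spearman correlation near 0.30 with the full count (n = 100), power fell by 2 to 3 points at mean 1.0 and by 7 to 18 points at means of 1.5 to 2.4.

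**The case against.** The strongest reply is that this is a descriptive table in an exploratory study. Protocol 7.2 plans no confirmatory hypotheses, and no visible test, group contrast or biomarker model uses these classes. A reader might infer that a planned comparison is underpowered; the documents do not support that. This part of the reply stands, and the power figures are conditional.

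A reader might also infer that exacerbation number is handled this way throughout. That cannot be shown. SAP 5.3, 7.6 and 9 are not in the public text, and the SAP history table mentions multivariate analyses defined in more detail. The uncut count may already be used there. The point therefore concerns the visible SAP 7.4.1.

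Third, the table fits the protocol's rule for count variables, total exacerbation days are kept as a number, and events are listed with dates. This stands in part. A full frequency table would meet the rule equally well, and neither the days nor the listing gives a mean number or rate per group. It does refute the inference that the mean is lost for good.

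Fourth, comparing a correctly specified negative-binomial test with a trend test mixes a gain from the model with a gain from the scale. That is right. The Mann-Whitney columns isolate the scale, and the loss is smaller.

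Finally, it is tempting to call the at least moderate and severe endpoints equally faulty. SAP 5.1 defines both by occurrence, so their tables do not fall short in the same way.

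**Conclusion.** The point holds for the visible SAP 7.4.1. A main outcome defined as a number is summarised in three classes that give neither the mean nor the rate per diagnosis group, and that do not separate 2 events from many. This follows from the text and needs no assumption.

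How much is hidden depends on event rates and dispersion that the documents do not give. Over 0.25 to 1.5 events per patient-year and dispersion 0.5 to 2, the top class holds 18% to 77% of patients and 62% to 97% of events. Loss of power arises only if contrasts are made on the cut scale. It is a few points at 3-year means of 0.5 to 0.75 and several tens of points at 2.4 or more, and smaller with a like-for-like rank test. The plan's stated sample-size figures are unaffected. This is a reporting and efficiency weakness that is cheap to correct, not an error that invalidates a planned inference.

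**What to change.** In SAP 7.4.1:

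- Keep the 0 / 1 / at least 2 table.
- Add, by diagnosis group, the full count distribution with mean, SD, median and quartiles.
- Add the exacerbation rate per patient-year with 95% CI from a negative-binomial model with subject group as factor and log follow-up time as offset. State which person-time is used, so that it matches the period over which events are counted (Protocol 5.7.1.1 ends it at Visit 7 or discontinuation, while 6.2.2 collects exacerbation status by telephone afterwards).
- Leave the A1ATD group (up to 20 patients) descriptive. Exacerbations are defined as related to underlying COPD, so the ex-smoking controls should contribute no events and the model can be limited to GOLD 1 to 3.
- Use the uncut count with the same offset in any analysis relating exacerbation number to biomarkers.
- Leave the two occurrence endpoints as tabulated; a rate of at least moderate exacerbations is an optional addition.

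The cost is SAP wording, a few table rows and one standard model. The events are already collected, so no new data are needed.

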6. GENERAL ANALYSIS DEFINITIONS

6.1 TREATMENT(S)

No treatment or investigational drug is administered to the subjects. All analyses will be presented based on the diagnosis group entered in the eCRF (ex-smoking controls, COPD GOLD 1, COPD GOLD 2, COPD GOLD 3, and COPD with A1AT deficiency (A1ATD)) as well as for COPD GOLD 1, 2, and 3 combined, unless otherwise specified. A reclassification of subjects into the above mentioned diagnosis groups will be done based on spirometry data at baseline to investigate the extend of misclassified subjects (see Section 9.6).

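### SAP 7.4.1 reports exacerbation duration as days summed over a subject's episodes, so the main outcome mixes episode length with episode count and follow-up time

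*SAP*

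**What the plan says.** Protocol 5.1.1 gives the third main outcome as "Number, duration and severity of exacerbations during the course of the study". Protocol 5.7.1.1 defines an exacerbation as a complex of lower respiratory symptoms "with duration of three days or more". It says that onset "will be defined as the onset of first recorded symptom", and it leaves the end of the episode to the investigator's judgment. Neither section says how the duration outcome is to be aggregated.

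SAP 5.1 splits the outcome into number, duration in days up to week 156, and two severity items. SAP 7.4.1 then sets the derivation of duration: "This endpoint will be calculated by the sum of episodes during the study and will be summarized descriptively". The next sentence fixes who is counted: "Duration of exacerbations will be summarized for subjects with at least one exacerbation". For number, the SAP says "This endpoint will be summarized descriptively by the following categories: 0 vs. 1 vs", the last category being two or more. SAP 6.1 sets the layout: "All analyses will be presented based on the diagnosis group entered in the eCRF", with GOLD 1 to 3 also combined.

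SAP 4.2 declares no change from the protocol's planned analyses. SAP 4.3 says that the SAP clarifies the main outcomes.

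**The concern.** A reader who sees a table of exacerbation duration by diagnosis group will take it to show how long exacerbations last. The SAP quantity does not show that. For each subject it is the number of episodes times their mean length. Restricting the table to subjects with at least one episode does not remove the count, because the mean number of episodes among such subjects still rises with the event rate.

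Observation time enters in the same way. Protocol 5.7.1.1 ends exacerbation collection at Visit 7 or the discontinuation visit, and SAP Section 7 treats subjects who finished week 104 without consenting to the third year as completers. Subjects therefore contribute different lengths of observation, and the sum is not adjusted for this.

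What is at stake is the interpretation of one of the six main outcomes listed in SAP 5.1: a gradient across groups could reflect frequency, length or follow-up, and the planned tables do not separate them.

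**Working it through.** The documents state no exacerbation rate, episode length or sample-size figure for this outcome, so there is no plan figure to reproduce. The rates and lengths below are assumptions. The direction of the effect does not depend on them; its size does.

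**1. Effect of event rate at constant episode length.** Let r be events per year, T years of follow-up, L = r × T, and d mean days per episode. If counts are Poisson, the mean count among subjects with at least one episode is L / (1 − exp(−L)). The SAP's mean duration is d times this. Take T = 3 and d = 12 in every group:

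| Rate per year | L | Episodes per subject with ≥1 | Reported days (× 12) |
|---|---|---|---|
| 0.3 | 0.9 | 0.9 / 0.593 = 1.52 | 18.2 |
| 0.6 | 1.8 | 1.8 / 0.835 = 2.16 | 25.9 |
| 1.0 | 3.0 | 3.0 / 0.950 = 3.16 | 37.9 |

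The ratio from top to bottom is 37.9 / 18.2 = 2.1, with no difference in episode length. With negative binomial counts and dispersion 1, the conditional mean count is 1 + L, that is 1.9, 2.8 and 4.0 episodes, giving 22.8, 33.6 and 48.0 days.

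**2. A second set of assumptions.** With d = 10 and T = 1092 / 365.25 = 2.99 years, Poisson counts give 13.3 days at 0.2 per year, 19.3 at 0.5, 31.5 at 1.0 and 45.4 at 1.5. A simulation with episodes of at least 3 days and mean 10 shows that the median of the summed days moves as well, from 11.0 at 0.2 per year to 28.6 at 1.0. Reporting medians would not cure the problem.

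**3. The order on episode length can reverse.** With the same T, 14-day episodes at 0.2 per year give 18.6 reported days, and 8-day episodes at 1.0 per year give 25.2. The group with the shorter episodes shows the longer 'duration'.

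**4. Effect of follow-up alone.** With d = 10 and 0.5 events per year, the reported figure is 12.7 days over 52 weeks, 15.8 over 104 and 19.3 over 156.

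**5. What can be recovered from the planned tables.** The mean burden per subject can be: it is the mean among subjects with an episode times the share of subjects with one. If 10% of a group have one 30-day episode, 0.10 × 30 = 3 days per subject. If 80% have two 10-day episodes, 0.80 × 20 = 16. Days per episode cannot be recovered, because the top count category is open. A subject in that category with 40 summed days may have had two 20-day episodes or four 10-day ones.

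**6. Behaviour of a per-episode summary.** In the simulation of step 2, the average of the per-subject mean days per episode stayed at 9.97, 10.00, 10.01 and 10.01 days for rates of 0.2, 0.5, 1.0 and 1.5. Its median drifted only from 9.1 to 9.7 over the same range.

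**The case against.** The best defence is that the SAP made a permitted choice and stated it openly. A reader might infer that the SAP departs from a protocol definition of duration as a per-episode quantity. The documents do not support that. Protocol 5.1.1 also fits cumulative time over the study; the three-day minimum in 5.7.1.1 is part of the case definition; and onset and end dates are needed for a sum as much as for a single episode. The protocol is open on this point and SAP 4.3 announces a clarification.

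A reader might also infer that episode count is used twice in the analysis. It is not: number and summed days are separate displays and are never combined. Nor is burden lost by leaving out subjects with no episodes. The denominator is stated, and SAP Section 7 includes N and mean in its End-of-Text summary statistics, so mean burden follows as in step 5.

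SAP 7.9 also plans a listing of medical events of special interest, which include COPD exacerbations, with start and end dates. Per-episode information will therefore exist, though as a listing and not as a summary by group.

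Finally, the outcome is described without a test, Protocol 7.2 plans no confirmatory hypotheses, and parts of the SAP that cannot be read, such as Section 5.3, may hold further derivations. All of this stands. It limits the consequence but does not make the planned table show episode length.

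**Conclusion.** The point holds as one of definition and interpretation. The figure that SAP 7.4.1 reports as duration rises with event rate and with follow-up even when episode length is constant, and no summary in the readable SAP gives episode length by group. Under the assumptions of step 1 the effect is about two-fold, 18 to 38 days between 0.3 and 1.0 events per year. These rates, the 12-day length and the Poisson model are illustrative; overdispersed counts give larger values.

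The consequence is a possible misreading of differences between diagnosis groups. No type I error or power is affected. The phrase 'sum of episodes' is itself elliptical. Given the unit, it is read here as summed episode days; read literally as a count, it would depend on episode number even more directly.

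**What to change.** In SAP 7.4.1:

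1. Define duration of exacerbations as days per episode, end minus onset plus 1, and summarise it as a per-subject mean among subjects with at least one exacerbation, by diagnosis group.
2. Rename the summed quantity 'total exacerbation days'. Report it per patient-year of observation for all subjects in the COPD and COPD with A1ATD groups, with zero days for those without an exacerbation. The patient-time should cover the same window in which episodes are counted. Without this basis, subjects who leave early or stop at week 104 would appear to have a low burden. Ex-smoking controls are left out because Protocol 5.7.1.1 ties an exacerbation to underlying COPD.

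The cost is a wording change and one extra descriptive table. Onset and end dates are already collected, and SAP 6.6.2 already has a rule for incomplete exacerbation dates. The summed figure would no longer stand as the duration outcome.
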